EBV-DNA	Epstein-Barr virus deoxyribonucleic acid
eGFR	Glomerular filtration rate
eCRF	Electronic Case Report Form
FAS	Full analysis set
FR	Frequent relapse
FDA	Food and Drug Administration
FK506	Tacrolimus
FK-BP-12	Tacrolimus binding protein-12
FK-BP-52	Tacrolimus binding protein-52
FK506-FKBP	Tacrolimus - tacrolimus binding protein
FRNS	Frequently relapsing nephrotic syndrome
GCP	Good Clinical Practice
g	Gram
GTP	Guanine nucleotide
HBV	Hepatitis B virus
HbsAg	Hepatitis B surface antigen
HbeAg	Hepatitis B E antigen

HbcAb	Hepatitis B core antigen
HCV	Hepatitis C virus
hr	Hour
ITT	Intentionality
LSMEAN	Least squares mean
LC-MS	Liquid chromatography-mass spectrometry
MMF	Mycophenolate mofetil
MPA	Mycophenolic acid
MPA-d3	Mycophenolic acid-d3
MPA-AUC	Mycophenolic acid - Area under curve
MI	Myocardial infarction
mg	Milligram
NR	No remission
PP	Per-protocol
PR	Partial remission
PML	Progressive multifocal leukoencephalopathy
PRCA	Pure red cell aplasia
PPS	Per-protocol set
SAS 9.4	STATISTICAL ANALYSIS SYSTEM Version 9.4
SD	Steroid-dependent
SDNS	Steroid-dependent nephrotic syndrome
SRNS	Steroid-resistant nephrotic syndrome
SCV	Site close-out visit
SAE	Serious adverse event
SOP	Standard Operation Procedures
SS	Safety set
Scr	Serum creatinine
TBiL	Total bilirubin
TIMP-1	Tissue inhibitor of metalloproteinase-1
TIA	Transient ischemic attack
WHO	World Health Organization
WBDC	Web-based data collection
α	Inspection level
β	Power of test
δ	Cut-off value

Protocol Abstract

1.1

Abstract

Title: Study of Tacrolimus vs Mycophenolate Mofetil in Pediatric Patients with Frequently Relapsing or Steroid-dependent Nephrotic Syndrome: a Prospective, Randomized, Multicenter, Open-label, and Parallel-arm Study on Efficacy and Safety

Objective: To evaluate the efficacy and safety of tacrolimus and mycophenolate mofetil in the treatment of frequently relapsing and steroid-dependent nephrotic syndrome in children, in order to provide a more effective and safer choice for the treatment of nephrotic syndrome in pediatric patients.

Design: Prospective, randomized, multicenter, open-label, and parallel-arm trial

Primary center: The Children's Hospital, Zhejiang University School of Medicine

Test drug name: Saikeping® Mycophenolate Mofetil Dispersible Tablets; Saifukai® Tacrolimus Capsules

Subjects: Pediatric patients with confirmed steroid-sensitive but frequently relapsing or steroid-dependent primary nephrotic syndrome

Treatment course: 1 year

Medication:

(1) Tacrolimus group: FK506 dose: 0.05-0.10 mg/kg/day, BID; in the induction period (the first six months after administration), the trough plasma concentration of tacrolimus is maintained at 5-10 ng/mL; in the maintenance period (the last six months after administration), the trough concentration is less than 5 ng/mL.

(2) Mycophenolate mofetil group: MMF dose: 20-30 mg/kg/day, BID; in the induction period (the first six months after administration), the plasma concentration MPA-AUC is maintained at 30-50 µg.h/mL; in the maintenance period (the last six months after administration), the MPA-AUC is ≤ 40 µg.h/mL.

(3) Prednisone dose: The initial dose is 1.0-1.5 mg/kg every other day or 0.5-0.75 mg/kg every day. The dose shall be reduced after 4 weeks by 0.25 mg/kg (every other day) or 0.125 mg/kg (every day) every 2-4 weeks. If the condition is stable, continue to reduce and maintain at 5mg (body surface area > 1 m²) and 2.5mg (body surface area < 1 m²) every other day.

Efficacy outcomes:

Primary observation outcomes: 1-year relapse-free survival

Secondary observation outcomes: Renal function; cumulative steroid dosage; blood pressure; height; body weight; blood lipids; hemoglobin; serum albumin; urinary protein/creatinine (morning urine); 24hr urinary protein quantification (applicable to subjects > 3 years old);

frequency of relapses; the time of the first relapse after enrollment; relapse-free rate in the first six months after enrollment; adverse reactions;

Safety outcomes: Changes of vital signs (respiration and heart rate), blood and urine routine, liver function, blood glucose, ECG, chest X-ray, and observation of clinically reported adverse events and adverse reactions.

[figure not shown]
Sample size: 270 cases. Including 135 cases in MMF Group, and 135 cases in FK506 Group.

Statistical analysis: SAS 9.4 software for data statistical analysis.

1.2

Research Plan

Research Plan

1.3

Clinical trial flow chart

Clinical trial flow chart

Items	Screening and enrollment period		Treatment and follow-up period							
	Screen (V0)	Visit 1 (V1)	Visit 2 (V2)	Visit 3 (V3)	Visit 4 (V4)	Visit 5 (V5)	Visit 6 (V6)	Visit 7 (V7)	Visit 8 (V8)	Visit 9 (V9)
Follow-up week	Day -30 - 0	Included	Day 7	Day 28	Day 56	Day 112	Day 168	Day 224	Day 280	Day 364
Sign the Informed Consent Form	√									
Inclusion/Exclusion Criteria		√								
Stop the original immunosuppressants after 2 weeks	\$	\$								
Randomized		√								
General data	√									
Medical history (course of disease, frequency of relapses in 1 year and 6 months before enrollment, steroid dosage)	√									
Vital signs	√	√	√	√	√	√	√	√	√	√

Items	Screening and enrollment period		Treatment and follow-up period							
	Screen (V0)	Visit 1 (V1)	Visit 2 (V2)	Visit 3 (V3)	Visit 4 (V4)	Visit 5 (V5)	Visit 6 (V6)	Visit 7 (V7)	Visit 8 (V8)	Visit 9 (V9)
Height and weight	√	√	√	√	√	√	√	√	√	√
Physical examination	√	⊙	√	√	√	√	√	√	√	√
Blood routine examination	√	⊙	√	√	√	√	√	√	√	√
Urine routine examination	√	⊙	√	√	√	√	√	√	√	√
Fasting blood glucose	√		√	√	√	√	√	√	√	√
Serum liver function	√	⊙	√	√	√	√	√	√	√	√
Blood lipid	√	⊙	√	√	√	√	√	√	√	√
Serum renal function	√	⊙	√	√	√	√	√	√	√	√
Blood EBV-DNA, and CMV antibody	√									√
24h urinary protein (>3 years old)	√	⊙	√	√	√	√	√	√	√	√
Urinary protein / creatinine	√	⊙	√	√	√	√	√	√	√	√
eGFR	√	⊙	√	√	√	√	√	√	√	√

Items	Screening and enrollment period		Treatment and follow-up period							
	Screen (V0)	Visit 1 (V1)	Visit 2 (V2)	Visit 3 (V3)	Visit 4 (V4)	Visit 5 (V5)	Visit 6 (V6)	Visit 7 (V7)	Visit 8 (V8)	Visit 9 (V9)
Tacrolimus concentration in plasma			√	√	√	√	√	√		√
Mycophenolic acid concentration in plasma			√				√			
Chest X-ray	√									√
ECG	√									√
Markers of hepatitis B and hepatitis C virus	√									
Examination of Mycobacterium tuberculosis and fungi	√									
Biological samples of blood and urine	√						√			√
Drug distribution and measurement		√	√	√	√	√	√	√	√	√
Guidance on the administration of test drug		√	√	√	√	√	√	√	√	√

Items	Screening and enrollment period		Treatment and follow-up period							
	Screen (V0)	Visit 1 (V1)	Visit 2 (V2)	Visit 3 (V3)	Visit 4 (V4)	Visit 5 (V5)	Visit 6 (V6)	Visit 7 (V7)	Visit 8 (V8)	Visit 9 (V9)
Clinical efficacy (relapse or no)			√	√	√	√	√	√	√	√
Concomitant medication	√	√	√	√	√	√	√	√	√	√
Adverse event			√	√	√	√	√	√	√	√
Record case report form	√	√	√	√	√	√	√	√	√	√

Remarks:

1. Liver function: ALT, TBiL, ALB; Renal function: creatinine, urea nitrogen, uric acid, Cystatin C;
2. Blood lipids: Triglycerides, cholesterol; Urinary protein / creatinine: morning urine; Markers of hepatitis B and hepatitis C virus: HBsAg, HBeAg, HBcAb, HCV;
3. Mycobacterium tuberculosis examination: T-sport; Fungal examination: fungal G test or other; Estimated glomerular filtration rate: $eGFR = K \times \text{height (cm)} / \text{serum creatinine (mg / dL)}$ (see Appendix);
4. Visit time window: ± 3 days for visit 2, and ± 7 days for other visits;
5. \$ items are applicable to the pediatric patients with combined use of other immunosuppressants before enrollment; © items are optional, depending on the judgment and decision of the investigators;
6. This research accepts the examination data from our hospital within 2 weeks before the screening period, and no repeated test is needed.

1. Background

Primary nephrotic syndrome, the most common glomerular disease in children, accounts for about 90% of the total nephrotic syndrome cases in pediatric patients^[1]. It is reported that the annual incidence rate of pediatric nephrotic syndrome is about 2-4/100000, and the prevalence rate is about 16/100000^[2, 3]. The statistics of hospitalized children in some provincial and municipal hospitals in China show that primary nephrotic syndrome accounts for about 20% of hospitalized children with urinary system diseases^[4]. Renal biopsy shows minimal lesions in more than 80% of patients. This disease can occur at any age, but it mostly occurs at the age of 2-6. It is more common in boys, with a male/female ratio of about 3:2. Since the 1950s, glucocorticoids have been recognized as the first-line treatment. About 80%-90% of pediatric patients with primary nephrotic syndrome can achieve complete remission after initial steroid treatment, but 76%-93% of the pediatric patients have relapses, of which 45%-50% show frequent relapses (FR) or steroid dependence (SD)^[5]. The relapses of proteinuria, especially frequently relapsing/steroid-dependent nephrotic syndrome, have always been a very difficult and urgent problem for clinicians. Some pediatric patients may have steroid resistance after repeated relapses and eventually develop into chronic dysfunction. The long-term or repeated use of steroids at high doses will lead to side effects such as obesity, growth inhibition, hypertension, diabetes, glaucoma, cataract, osteoporosis and serious infection. Its combined use with traditional immunosuppressants such as cyclophosphamide and cyclosporine A (CSA) will bring some serious irreversible side effects. Therefore, it is particularly important to explore new immunosuppressants and their application schemes.

Tacrolimus is a 23-membered macrolide antibiotic extracted from the fermentation of *Streptomyces*. It was used clinically in 1989 for the first time, and officially used in the United States after being approved by the U.S. Food and Drug Administration (FDA) in 1995. It was registered as an imported drug in China in 1998 and gradually used in clinical application. Tacrolimus, a new type of calcineurin inhibitor, can be combined with FK506 binding protein-12 (FK-BP-12) and FK506 binding protein-52 (FK-BP-52) receptors in the cytoplasm of T lymphocytes *in vivo* to form FK506-FKBP complex, with a function of inhibiting the phosphorylase activity of calmodulin phosphatase, thus inhibiting the proliferation of T lymphocytes. This indirectly affects the production of B lymphocytes and antibodies, and finally causes immunosuppression^[6] to achieve the purpose of treating glomerular diseases. Its immunosuppressive effect is 10 - 100 times that of cyclosporine A^[7]. In addition to its strong immunosuppressive effect, tacrolimus also has its non-immunosuppressive effects: (1) It can produce hormone-like effect or reduce the dosage of hormone; (2) It can significantly down-regulate the expression of tissue inhibitor of metalloproteinase-1 (TIMP-1), while CsA can

up-regulate the expression of TIMP-1. Therefore, tacrolimus shows weaker effect on tissue fibrosis than CsA; (3) It can inhibit platelet aggregation, reduce thrombosis and reduce inflammatory reaction^[8]; (4) It has podocyte protection effect. The studies by Li Xiayu et al.^[9] have shown that as compared with cyclophosphamide, tacrolimus can induce the remission of nephrotic syndrome more quickly in adult patients with steroid dependence and minimal lesion in pathology. About 72.7% of patients using tacrolimus can successfully stop the application of steroid. In the treatment of steroid-dependent or steroid-resistant focal segmental sclerosis, the studies by Hong Ren et al.^[10] have shown that tacrolimus and cyclophosphamide have similar effects, both of which can reduce urinary protein, improve renal function and blood albumin level. The previous clinical studies of the Department of Nephrology of the Children's Hospital, Zhejiang University have also found that tacrolimus can effectively reduce the frequent relapses or the relapse frequency of steroid-dependent nephrotic syndrome, and down-regulate the total amount of hormone use.

Mycophenolate mofetil (MMF) is a precursor of mycophenolic acid (MPA). Mycophenolic acid is a reversible and non-competitive inhibitor of hypoxanthine monophosphate dehydrogenase, a rate limiting enzyme in purine synthesis. It can significantly inhibit the classical synthesis pathway of guanine nucleotide (GTP), without any impact on other synthesis pathways and remedial synthesis pathways.^[11] MMF will not significantly damage liver, kidney or bone marrow cells, and can avoid cytotoxic damages caused by other immunosuppressants^[12]. MMF can quickly inhibit the synthesis of antibodies, and effectively inhibit the secretion of surface adhesion molecules, to play the pharmacological role in anti-inflammatory response. In addition, MMF can also significantly inhibit the proliferation rate of vascular smooth muscle cells and endothelial cells, inhibit the production of cell adhesion molecules and aggregation of a large number of leukocytes near the inflammatory tissues, enhance its pharmacological effect of immunosuppression by inducing lymphocyte apoptosis, and finally significantly reduce the degree of renal parenchyma damage and avoid the occurrence of glomerulosclerosis^[13]. Animal researches have also confirmed that MMF can play a great role in the process of activation under the activation of inflammatory cells, transdifferentiation of myofibroblasts and massive aggregation of extracellular matrix, so as to prevent the pathological process of renal interstitial fibrosis^[14]. In 1998, Briggs et al. first used MMF in the treatment of adult steroid-resistant or steroid-sensitive but recurrent nephrotic syndrome, showing a good curative effect^[15]. Then, many studies at home and abroad have shown that mycophenolate mofetil can reduce the relapse frequency of frequently relapsing nephrotic syndrome and reduce the dosage of steroid. Recent studies by Gellermann et al.^[16] have shown that cyclosporine A is better than mycophenolate mofetil in reducing the relapse frequency of frequently relapsing nephrotic syndrome, but mycophenolate mofetil is significantly better than cyclosporine A in protecting the renal function. In short, it is believed that MMF can effectively

reduce the relapse rate of nephropathy, reduce and even stop the steroid use, with less adverse reactions and no nephrotoxicity. It is an effective and safe immunosuppressant for the treatment of FRNS in pediatric patients.

In addition, domestic and foreign expert guidelines, such as *KDIGO Clinical Practice Guideline for Glucurulonephritis (2012)*, *Evidence-based Guideline for the Diagnosis and Treatment of Steroid-resistant Nephrotic Syndrome (2016)* and *Evidence-based Guideline for the Diagnosis and Treatment of Steroid-sensitive and Recurrent/Dependent Nephrotic Syndrome in Pediatric Patients (2016)*, all recommend tacrolimus and mycophenolate mofetil for frequently relapsing/steroid-dependent nephrotic syndrome^[17-19]. Among these two types of drugs, tacrolimus with the dual effects of immunosuppression and podocyte protection, is more widely used in Department of Nephrology, and mycophenolate mofetil has also gradually obtained the attention from nephrologists in recent years because of its non-nephrotoxicity, less adverse reactions and high safety. However, currently there are no multicenter studies comparing the efficacy of tacrolimus and mycophenolate mofetil in pediatric patients with frequently relapsing/steroid-dependent nephrotic syndrome at home and abroad. Therefore, the purpose of this research is to observe the efficacy and safety of tacrolimus and mycophenolate mofetil in the treatment of frequently relapsing/steroid-dependent nephrotic syndrome in pediatric patients with a prospective, randomized, multicenter, open-label and parallel-arm approach, and evaluate their safety, hoping to provide a more effective and safe treatment scheme for frequently relapsing/steroid-dependent nephrotic syndrome in pediatric patients.

2. Purpose

2.1 To observe the efficacy of test drugs on the frequently relapsing or steroid-dependent nephrotic syndrome in pediatric patients

Efficacy outcomes:

Primary observation outcomes: 1-year relapse-free survival

Secondary observation outcomes: Renal function; cumulative steroid dosage; blood pressure; height; body weight; blood lipids; hemoglobin; serum albumin; urinary protein/creatinine (morning urine); 24hr urinary protein quantification (applicable to subjects > 3 years old); frequency of relapses; the time of the first relapse after enrollment; relapse-free **survival** in the first six months after enrollment; adverse reactions;

2.2 To observe the safety outcomes of test drugs

Changes of vital signs (respiration and heart rate), routine blood and urine tests, liver function, renal function, blood glucose, ECG, chest X-ray, and observation of clinically reported adverse events and adverse reactions.

3. Design basis, type, principle and case allocation

3.1 Design basis

- *Pharmaceutical Administration Law of the People's Republic of China*, 2001
- *Drug Registration Regulation*, 2007
- *Good Clinical Practice (GCP)*, 2003
- *Declaration of Helsinki*, 2008
- Results of pharmacodynamic and toxicological studies of tacrolimus and mycophenolate mofetil ingredients, and current clinical trial experience

3.2 Design type

This trial adopts a prospective, randomized, multicenter, open-label and parallel-arm clinical research method. The whole observation period is 1 year for this trial. See P12 “Clinical trial flow chart” for details.

3.3 Design principle and case allocation

3.3.1 Difference analysis

In this research, Logrank method is used to compare the difference of 1-year relapse-free survival between the two groups.

Eligible patients will be randomly divided into FK506 Group or MMF Group at the ratio of 1:1. The random codes are generated by the computer and the random envelopes are made according to these random codes. Grouping information is attached in each envelope. Each code is provided with a corresponding random envelope, and the random numbers are given to the subjects from small to large according to the time sequence when the subjects meet the inclusion criteria. The corresponding random envelopes can only be opened when grouping. Any random number falling off midway after use cannot be used again.

3.3.2 Determination of the number of cases

It is estimated that 1-year relapse-free survival is 0.56 in MMF Group, and 0.70 in FK506 Group. The enrollment time of this research is expected to be 2 years, and the total time of this research is 3 years, with a test level $\alpha = 0.05$, and a power of test $1 - \beta = 80\%$. It is estimated to have 114 patients in MMF group and 115 patients in FK506 group, with a total of 229 patients (see Appendix 4 for details). With the consideration of 15% loss of follow-up, a total of 270 patients are needed, including 135 patients in each group.

4. Selection of cases

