Appendix 4 Parameters and results sample size calculation

Parameters and results in sample size calculation:

2019/4/30 10:57:07 1

Logrank Test Analysis

Numeric Results in Terms of Sample Size when the Test is Two-Sided and T0 is 1

Power	N1	N2	N	Haz Ratio (HR)	Ctrl Prop Surv (S1)	Trt Prop Surv (S2)	Acc-rual Pat'n	Acc-rual Time/Total Time	Ctrl Loss	Trt Loss	Ctrl to Trt	Trt to Ctrl	Alpha	Beta
0.8009	114	115	229	0.6151	0.5600	0.7000	Equal	2 / 3	0.0000	0.0000	0.0000	0.0000	0.0500	0.1991

References

Lakatos, Edward. 1988. 'Sample Sizes Based on the Log-Rank Statistic in Complex Clinical Trials', Biometrics, Volume 44, March, pages 229-241.
 Lakatos, Edward. 2002. 'Designing Complex Group Sequential Survival Trials', Statistics in Medicine, Volume 21, pages 1969-1989.

Report Definitions

Power is the probability of rejecting a false null hypothesis. Power should be close to one.
 N1|N2|N are the sample sizes of the control group, treatment group, and both groups, respectively.
 E1|E2|E are the number of events in the control group, treatment group, and both groups, respectively.
 Hazard Ratio (HR) is the treatment group's hazard rate divided by the control group's hazard rate.
 Proportion Surviving is the proportion surviving past time T0.
 Accrual Time is the number of time periods (years or months) during which accrual takes place.
 Total Time is the total number of time periods in the study. Follow-up time = (Total Time) - (Accrual Time).
 Ctrl Loss is the proportion of the control group that is lost (drop out) during a single time period (year or month).
 Trt Loss is the proportion of the treatment group that is lost (drop out) during a single time period (year or month).
 Ctrl to Trt (drop in) is the proportion of the control group that switch to a group with a hazard rate equal to the treatment group.
 Trt to Ctrl (noncompliance) is the proportion of the treatment group that switch to a group with a hazard rate equal to the control group.
 Alpha is the probability of rejecting a true null hypothesis. It should be small.
 Beta is the probability of accepting a false null hypothesis. It should be small.

Numeric Results in Terms of Events when the Test is Two-Sided and T0 is 1

Power	Ctrl Evts E1	Trt Evts E2	Total Evts E	Haz Ratio (HR)	Ctrl Prop Surv (S1)	Trt Prop Surv (S2)	Acc-rual Pat'n	Acc-rual Time/Total Time	Ctrl Loss	Trt Loss	Ctrl to Trt	Trt to Ctrl	Alpha	Beta

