4.2.2 Determination of the number of cases

It is estimated that 1-year relapse-free survival is 0.56 in MMF Group, and 0.70 in FK506 Group. The enrollment time of this research is expected to be 2 years, and the total time of this research is 3 years, with a test level $\alpha = 0.05$, and a power of test $1 - \beta = 80\%$. It is estimated to have 114 patients in MMF group and 115 patients in FK506 group, with a total of 229 patients. With the consideration of 15% loss of follow-up, a total of 270 patients are needed, including 135 patients in each group.

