8.1.3. Primary efficacy analysis

Logrank test is used for the analysis of relapse-free survival rate which is then used as a covariate for stratification by Sites. HR and its 95% confidence interval (CI) are calculated with Cox proportional hazard model to estimate the efficacy, the confidence interval is applied to verify the superiority of the experimental group and the control group, with a cut-off value of 1 (risk ratio). The model incorporates the same covariate as the Logrank test for fitting, and the definition method of covariates is also the same as that in the Logrank test. The Kaplan-Meier curve of relapse-free survival is drawn by treatment groups. The 1-year relapse-free survival rate and its confidence interval are then calculated.

Calculation rules for the main efficacy indicators:

- If relapse occurred within 9 visits (within 364 ± 7 days) or unscheduled visits within 365 days of randomization, defined as the occurrence of endpoint events. Time of relapse = date of relapse - Random date + 1, calculated by days.
- If the visit stipulated in the protocol was not completed within 9 visits (within 364 ± 7 days) due to loss of follow-up midway or withdrawal or other reasons, it is defined as censoring. Time of

censoring = date of withdrawal - random date + 1, calculated by days.

- If the visit stipulated in the protocol was not completed within 9 visits (within 364 ± 7 days) due to death in the trial, it is defined as censoring. Time of censoring = Death date - random date + 1, calculated by days.
- If the visit stipulated in the protocol was completed and there is no relapse within 9 visits (within 364 ± 7 days), it is defined as censoring. Time of censoring = date of visit 9 (within 364 ± 7 days) - random date + 1, calculated by days.

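### The 80% power assumes each child is followed for 1 to 3 years; with the 1 year the trial provides, it is about 61–65%

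*Protocol*

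**What the plan says.** **Sample size.** Protocol 3.3.2 assumes 1-year relapse-free survival of 0.56 on MMF and 0.70 on tacrolimus, with a test level of 0.05 and 80% power. On timing it says: "The enrollment time of this research is expected to be 2 years, and the total time of this research is 3 years". SAP 4.2.2 repeats the result: "It is estimated to have 114 patients in MMF group and 115 patients in FK506 group, with a total of 229 patients". Both documents then allow for 15% loss and arrive at 270, 135 per arm.

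**Program output.** Protocol Appendix 4 is headed "Numeric Results in Terms of Sample Size when the Test is Two-Sided and T0 is 1". It lists equal accrual, accrual/total time of 2 / 3, zero loss in both arms, hazard ratio 0.6151, power 0.8009, and 133.8 expected events (76.6 MMF, 57.2 tacrolimus). Its definitions include: "Total Time is the total number of time periods in the study. Follow-up time = (Total Time) - (Accrual Time)".

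**Conduct and analysis.** Protocol 3.2 says: "The whole observation period is 1 year for this trial". Protocol section 6 gives one year of treatment in both arms, and the flow chart ends at Visit 9, Day 364. SAP 8.1.3 counts a relapse as an event only up to Visit 9, or within 365 days of randomisation for an unscheduled visit. For a child who completes without relapse it sets: "Time of censoring = date of visit 9 (within 364 ± 7 days)".

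**The concern.** Two years of enrolment and three years in total correctly describe the trial's calendar. In the log-rank program, however, they also fix how long children stay at risk. Total time minus accrual time (3 − 2 = 1 year) is follow-up after the last entry, so it is the minimum. A child entering on the first day is counted as at risk for three years. The trial stops observing that child after one.

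The power of a log-rank test depends on the number of events. If the relapses expected in years 2 and 3 are never observed, the 80% does not describe this design. At stake is how a non-significant primary result is read: the documents would present it as coming from a trial with a 20% chance of missing the planned difference, when the chance is much larger.

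**Working it through.** **Inputs.** 1-year relapse-free survival 0.56 and 0.70, and two-sided alpha 0.05 (Protocol 3.3.2, Appendix 4). Group sizes 114 and 115; 135 per arm after allowance for loss. Accrual 2 years, total 3 years. One year of observation per child (Protocol 3.2, SAP 8.1.3).

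**Hazards.** Exponential relapse times are implied by the plan's single hazard ratio.
- MMF: λ₁ = −ln 0.56 = 0.5798 per year
- Tacrolimus: λ₂ = −ln 0.70 = 0.3567 per year
- HR = 0.3567 / 0.5798 = 0.6151, as printed

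**Step 1: reproduce Appendix 4.** With uniform accrual over R = 2 of T = 3 years, the probability of an observed event is 1 − [exp(−λ(T−R)) − exp(−λT)] / (λR).
- MMF: 0.6685; 114 × 0.6685 = 76.2
- Tacrolimus: 0.4995; 115 × 0.4995 = 57.4
- Total 133.7, against 133.8 printed

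Schoenfeld power = Φ(|ln HR| × √(E/4) − 1.96) = Φ(0.4859 × √(133.7/4) − 1.96) = 80.2%, against 0.8009 printed. Also 229 / 0.85 = 269.4, rounded up to 270. The plan's figures therefore reproduce, but only with 1 to 3 years of follow-up per child.

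**Step 2: one year per child.** The event probabilities are 1 − 0.56 = 0.44 and 1 − 0.70 = 0.30.
- *229 evaluable:* 114 × 0.44 + 115 × 0.30 = 50.16 + 34.50 = 84.7 events. Power = Φ(0.4859 × √(84.66/4) − 1.96) = 60.8%.
- *270 enrolled, 15% lost at a constant rate over the year (assumed; the plan gives no timing):* loss hazard μ = −ln 0.85. The event probability is λ/(λ+μ) × [1 − exp(−(λ+μ))]. Events 55.3 + 37.6 = 92.8; power 64.8%.
- *270 enrolled, no loss:* 135 × 0.44 + 135 × 0.30 = 99.9 events; power 68.0%.

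**Step 3: other methods.** Simulated values are from 10,000 trials each.

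| Design | Events | Schoenfeld | Lakatos-type | Freedman | Simulated |
|---|---|---|---|---|---|
| Appendix 4 (1–3 years), 229 | 133.7 | 80.2% | 80.0% | 78.7% | 79.6% |
| 1 year, 229 evaluable | 84.7 | 60.8% | 60.2% | 59.2% | 60.3% |
| 1 year, 270, 15% loss | 92.8 | 64.8% | 64.0% | 63.1% | 64.1% |
| 1 year, 270, no loss | 99.9 | 68.0% | 67.2% | 66.3% | 67.0% |

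A plain comparison of one-year proportions, which uses no hazard model, gives 59.4% with 114/115 and 66.5% with 135/135.

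**Step 4: what the trial can detect.** For 80% power, |ln HR| = (1.960 + 0.842) × 2 / √E. With E = 92.8 this is 0.582, so HR ≈ 0.56. That corresponds to 0.56 against 0.56^0.56 ≈ 0.72.

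**Step 5: what 80% at HR 0.615 would take.** Schoenfeld needs 133 events. At an average one-year event probability of 0.37, that is 133 / 0.37 ≈ 360 evaluable children, and 133 / 0.37 / 0.85 ≈ 423 enrolled. Freedman's formula (139 events) gives about 376 and 442.

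**The case against.** The arithmetic in Appendix 4 is correct for its inputs, and the type I error, the hazard ratio and its confidence interval are untouched. A reader of a null result would see the imprecision in the interval that SAP 8.1.3 already requires. All of that stands. It limits the harm to the power claim but does not make the claim true.

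A second point is that 61–65% looks too precise. Loss timing is unstated. If all 15% left at entry there would be 84.9 events (61.0%); if all left at the very end, close to 99.9 (68.0%). Across formulas the span is about 59–68%. This is fair as to presentation, but no variant comes near 80%.

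Could longer follow-up supply the missing relapses? Protocol 11.3.5 and SAP 8.1.5 mention efficacy in long-term follow-up after the trial, but only among the other analyses, with descriptive statistics and chi-square or Fisher tests. It does not enter the primary comparison. The move from 229 to 270 does not help either, because those 41 places are the loss allowance.

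Finally, SAP 4.1 describes enrolment as completed, so a correction restores no power, and rewriting the protocol would blur the record of how 270 was chosen. That bears on how the correction is made. It is no reason to leave a wrong figure in place.

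**Conclusion.** The concern holds. The program's follow-up input does not match the design. With one year per child, the plan's own assumptions give about 85–93 relapses instead of 133.8, and power of about 61–65% instead of 80%. The chance of missing a true 0.56 against 0.70 difference is about 35–39%, not 20%. The most favourable case, all 270 followed with no loss, gives 68%.

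The figures rest on the plan's survival rates, on exponential relapse times and, for the 93, on loss at a constant rate over the year. The 84.7 needs neither of the last two assumptions; it follows directly from the one-year rates. The ±7-day window at Visit 9 does not change the result materially.

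**What to change.** Rerun the calculation with one year of follow-up for every child, and correct Protocol 3.3.2, Appendix 4 and SAP 4.2.2. With enrolment complete, a dated correction that keeps the record of how 270 was chosen would serve. It should state:
- about 85–93 expected relapses, with the assumption about loss timing (99.9 if none are lost);
- power of about 61–65% at a hazard ratio of 0.615 (68% with no loss);
- the hazard ratio detectable with 80% power, about 0.56.

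No extra enrolment is asked for. The cost is one program run and a few sentences, and the stated power becomes less favourable.

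A secondary option is to add baseline values already collected to the primary Cox model: relapses in the previous year (SAP Table 7) and FRNS or SDNS diagnosis (SAP Table 18). This could recover some power for the Cox confidence interval that SAP 8.1.3 uses to judge superiority. It would not change the power of the log-rank test. It would also alter the meaning of the hazard ratio and depart from the SAP's rule that both analyses use the same covariate. The gain is unknown, because the documents give no prognostic strength for these variables. If adopted in this open-label trial, it must be fixed before outcomes by arm are examined. The correction of the power statement does not depend on it.
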